## Study Design and Methods

**We propose to conduct a proof of concept clinical trial to test if administration of losartan augments CFTR function *in vivo* in patients who are on Orkambi™ or Symdeco™.** The goal of our pilot clinical trial is to examine the ability of losartan on CFTR (primary hypothesis) and possibly BK rescue/augmentation (secondary hypothesis) in patients homozygous for F508del on Orkambi™ or Symdeco™ therapy. The additional benefit for BK channels could be important but is harder to measure *in vivo*. Towards this end, however, we will assess CaCC/BK activity together as the response to ATP during NPD measurements, even though this is not an accurate reflection of either channel on its own.

**Note that ATP-induced changes in NPD in CF patients are higher than in normal subjects because *in vitro* data show that this response is increased in the *absence* of BK activity. Thus, the expectation here is that the rescue of BK activity with losartan will *DECREASE* NPD responses to ATP.**

**Primary hypothesis:** Losartan treatment for 12 weeks will improve CFTR conductance as measured by NPD in patients on Orkambi or Symdeco therapy. We expect that compared to placebo,  $\Delta$ NPD in response to 0 Cl/isoproterenol will change by more than -4 mV using the most polarized nostril each time.

**Secondary hypotheses:** Losartan treatment for 12 weeks will improve BK and CaCC activity as assessed by a decrease of changes in NPD to ATP exposure. Furthermore, losartan will reduce nasal cytokine levels and systemic inflammatory markers.

**Study plan:** Details are seen in Figure 2 and the study table. Briefly, 36 patients with CF, > 12 years of age, who are homozygous for F508del and have been on treatment with Orkambi™ or Symdeco™ for at least 3 months will be recruited for this trial. This trial will be randomized 1:1 with placebo (n=18 for each group). After signing informed consent at the screening visit, we will perform spirometry, determine sweat chloride, take blood (see below), and test for pregnancy where applicable. Since losartan has teratogenic effects, we will enforce strict birth control in female participants (see Potential Risk section.)

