## **STATISTICS AND POWER ANALYSIS**

**Randomization:** Upon eligibility, a statistician randomizes all subjects in a 1:1 ratio to the placebo or losartan treatment group and informs the research pharmacy. Participants will be stratified by site during randomization.

**Design:** The basic study design consists of random assignment of patients to one of two treatment arms: losartan or placebo. Data will be collected at the visits as outlined above.

**Analysis:** Primary endpoint: A t-test will be used as preliminary data analysis. For the formal analysis, mixed effects models model will be used for analysis to accommodate the paired measures nature of the design, as well as missing values under the MAR assumption. We will determine the final analytic approach based on the final available data. Examination of baseline differences on key variables between subjects remaining and those lost-to-follow-up will also be conducted. The first set of analyses will not adjust for dropouts. Only cases with complete data will be included.

Secondary endpoints: Prior to analysis, we will investigate the distributional properties of the defined outcome measures - such as CaCC/BK activity, change in sweat chloride concentration, FEV1, changes in serum inflammatory markers, etc. Necessary transformations such as logarithmic or square root will be applied to satisfy normality assumptions if necessary. Baseline values of all variables will be examined, and estimates of baseline means and changes over time will be provided. The statistical analysis will consist of descriptive statistics associated with outcome measure (mean change or mean difference pre and post treatment) for two treatments. Means at baseline, 6 and 13/14 weeks, for each outcome, as well as the change over time will be provided, as well as the corresponding estimates of variability, and 95% confidence intervals will be constructed. t-tests for comparisons of the changes over the period between treatments will be conducted. However, the primary focus for this analysis is to obtain reliable estimates of the mean changes and variability, which will be useful for designing further investigation focused and specifically powered for comparing these outcomes. P-value will be significant if  $< 0.05$ . All tests will be two-tailed. The SAS statistical software package version 9.3 (Cary, NC) will be used for all statistical analyses.

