## **Removal of Subjects from Study**

A subject withdrawal is defined as a discontinuation from the study for any reason. Subjects may withdraw or be withdrawn from this study for the following reasons:

- At their own request or at the request of their authorized representative at any time for any reason
- If, in the investigator's opinion, continuation in the study would be detrimental to the subject's well-being

Also subjects must be withdrawn from the study for the following reasons:

- Subjects with an occurrence of a concomitant disease, or any medical condition which, either because of its severity or duration or necessary change in treatment, contravenes the condition of the study or puts the patient at unnecessary risk or harm.
- Subjects with an occurrence of an AE/SAE which in the opinion of the investigator and/or subject requires termination of treatment. For example, skin rashes, palpitations or other moderate or severe adverse events (interference with usual daily activities) without other clear explanation should warrant immediate cessation of treatment and notification of study personnel.
- Subjects who are noncompliant with the protocol per the investigator's discretion
- Pregnancy
- Severe CF exacerbation during the study as by investigators' discretion.

Subjects who terminate the clinical study prematurely, either at their own request or on the recommendation of the clinical investigator, will be considered early terminations. Subjects who withdraw from the study will not be replaced. Subjects who are discontinued from the study will be requested to return for Early Discontinuation and perform procedures as for visit 8.

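### The plan does not say whether its complete-case rule governs the primary NPD result, and it leaves the final method to be chosen on the data

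*Combined protocol and SAP*

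**What the plan says.** The primary-endpoint paragraph under Statistics and Power Analysis makes these statements, in this order:

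1. A t-test is the preliminary analysis.
2. The formal analysis is a mixed-effects model, chosen to suit paired measurements "as well as missing values under the MAR assumption".
3. "We will determine the final analytic approach based on the final available data".
4. Patients who stay and patients lost to follow-up are compared at baseline.
5. A first set of analyses does not adjust for dropout.
6. "Only cases with complete data will be included".

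No second set is described, and neither the analysis population nor complete data is defined. Elsewhere the protocol gives the size ("This trial will be randomized 1:1 with placebo (n=18 for each group"), the expected effect (0 Cl⁻/"isoproterenol will change by more than -4 mV using the most polarized nostril each time") and the rule for leavers: "Subjects who withdraw from the study will not be replaced". The schedule in Appendix 1 places NPD at visits 1, 5 and 7. Patients who stop early are asked back for the visit 8 procedures, which include no NPD.

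**The concern.** A likelihood-based mixed model earns its MAR justification by using the measurements of patients who later drop out. Restricted to complete cases, it has no missing values left to handle, and its validity needs a stronger assumption about who leaves. The paragraph states both rules and does not say which one yields the primary result. The sentence deferring the final approach means that the choice could be made after the outcome data exist.

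The trial states a primary hypothesis and tests it formally ("All tests will be two-tailed", at the 0.05 level), with 36 patients and no replacement. Which patients enter the primary estimate should therefore not be open to two readings.

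**Working it through.** **1. The two readings.** Narrow: the complete-case sentence continues the one before it and covers only the first set, plausibly the t-test. The mixed model is then untouched. Broad: it covers the whole primary analysis and cancels the reason given for the mixed model. On either reading, the final approach stays open until the data are in.

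**2. Who is affected.** With NPD at visits 1, 5 and 7 and none at visit 8:

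| Patient | NPD available | Complete-case | Mixed model, all data |
|---|---|---|---|
| Leaves before visit 5 | baseline | dropped | adds little |
| Leaves between visits 5 and 7 | baseline, visit 5 | dropped | visit 5 used |
| Misses visit 5 only | baseline, visit 7 | depends on the missing definition | used |

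**3. Implied SD.** The available text shows neither an SD nor a target power, so 36 cannot be reproduced. (The power calculation that other sections refer to may have been lost in text extraction; this is not counted against the plan.) Solving SD = 4 / [(1.960 + z) × √(2/18)] for 18 per arm and two-sided 0.05:
- 80% power: 4 / (2.802 × 0.3333) = 4.28 mV (4.16 by the t distribution)
- 90% power: 4 / (3.242 × 0.3333) = 3.70 mV (3.60 by t)

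**4. Bias.** Each scenario simulated 4,000 trials of 18 per arm with NPD at baseline, week 6 (visit 5) and week 13 (visit 7). Assumptions: true effect −2 mV at week 6 and −4 mV at week 13; SD of change 3.7 or 4.28 mV; within-patient correlation 0.3, 0.5 or 0.7; dropout only after week 6. The complete-case estimator is the difference in mean change. The MAR estimator regresses week-13 NPD on arm, baseline and week-6 NPD among those observed, then averages the predictions over everyone. With c the week-6 change, the dropout probabilities were:
- losartan only: logistic(−1.2 + 1.5(c + 2)/SD), placebo 10%
- placebo only: logistic(−1.5 + 1.5c/SD), losartan 10%
- both arms: logistic(−1.6 + 1.5(c + 1)/SD)

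| Dropout after week 6 | Approx. loss, losartan / placebo | Complete-case (mV) |
|---|---|---|
| Poor responders, losartan only | 30% / 10% | −4.59 to −4.70 |
| Poor responders, placebo only | 10% / 25% | −3.34 to −3.49 |
| Same rule, both arms | 20% / 30% | −3.74 to −3.81 |
| Random | 20% / 20% | −3.98 to −4.02 |
| Unrelated to outcome | 25% / 5% | −3.94 to −4.05 |

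The MAR estimate lay between −3.95 and −4.05 throughout. The outcome-dependent rows are off by 4.00 − 3.81 = 0.19 mV at least and 4.70 − 4.00 = 0.70 mV at most, or 5% to 18% of 4 mV. With no true effect, two other losartan-only dropout rules gave complete-case estimates of −0.37 and −0.52 mV, against about 0 for the MAR estimate.

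**5. Precision.** At SD 4.28 and 20% random dropout, the empirical standard error was 1.59–1.61 mV complete-case and 1.54–1.55 mV for MAR. At the midpoints, (1.60/1.545)² = 1.07, about 7% more information. With SD 4.16, correlation 0.5–0.6 and 10% random dropout, the SDs of three estimators were about 1.45–1.48 (unadjusted change), 1.3 (complete-case adjusted for baseline) and 1.3 (likelihood adjusted for baseline). Nearly all of that gain comes from baseline adjustment, not from the incomplete patients.

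**The case against.** The strongest reply is that the narrow reading is the natural one. The sentence follows a statement about a first set of analyses, the t-test is called preliminary and the mixed model formal, and a t-test on change needs complete pairs anyway. A reader might infer that the plan has settled on a complete-case primary analysis; the text does not establish that. A reader might also infer that anyone missing week 6 is excluded. That presumes a definition of complete data that the plan does not give; a paired set could need only baseline and visit 7.

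The bias scenarios are chosen ones. Traces are read centrally and blinded to arm, and NPD response is not a listed reason for withdrawal. Adverse-event withdrawals at the week-1 dose step leave only a baseline NPD, so the mixed model cannot rescue them, and MAR does not correct dropout that observed NPD fails to explain. Baseline adjustment alone cut the complete-case bias from about 0.67 to about 0.36–0.41 mV when losartan-only dropout was outcome-dependent (26% vs 5%). The trial is a proof of concept, and its authors do not expect attrition to be limiting.

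All of this lowers the severity. It does not remove the point. The scope of the sentence is unstated, no dropout-adjusted set is described, and the final approach is explicitly deferred. Withdrawal for adverse events, noncompliance or severe exacerbation could differ by arm or track response, so dropout unrelated to outcome cannot be assumed.

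**Conclusion.** The concern stands as an unresolved scope together with a post-data choice of method. It is a should-fix.

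If the complete-case rule governs the primary result, the bias is roughly 0.2 to 0.7 mV of a 4 mV effect when dropout depends on observed NPD, and not material when dropout is unrelated to outcome. These sizes rest on assumed SDs, correlations and dropout rates; the documents give none.

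Two stronger conclusions are not supported:

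- **That the bias favours losartan.** It does so only if poor responders leave the losartan arm. Loss from placebo, or the same rule in both arms, biases against losartan.
- **That the mixed model would restore lost power.** At SD 4.28, power falls from 80.1% with 18 per arm to 75.3% with 16 and 69.6% with 14 (normal approximation). That compares with having no missing data at all, and step 5 shows that most of the loss is not recoverable.

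The case rests on validity and pre-specification, not on precision.

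**What to change.** Before unblinding, revise the primary-endpoint paragraph as follows:

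- Name one primary analysis: a mixed model on all randomised patients with any NPD measurement, analysed as randomised and using all available visits. The primary contrast is the losartan–placebo difference at visit 7.
- State how baseline NPD enters. Modelled as an outcome with a common mean across arms, it keeps patients who have only a baseline value in the model; as a covariate, only patients with a later NPD contribute. Include site, since randomisation is stratified by it.
- For the primary endpoint, delete "We will determine the final analytic approach based on the final available data". The study-drug section lists the biostatistics core among those unblinded, so the decision should be dated and recorded before anyone sees NPD results by arm.
- Limit "Only cases with complete data will be included" to a t-test labelled preliminary or sensitivity, and define complete data there as baseline plus visit 7 NPD.

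The cost is wording and minor analysis work. No extra patients, visits or measurements are needed.

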### Endpoints

- Primary endpoint
  - $\Delta$ NPD with 0 Cl/isoproterenol as a measure of CFTR activity in losartan treatment compared to placebo (15), done according to standard procedures (16); for power calculation, see below. All traces will be read blinded at the Cincinnati Children's Hospital Medical Center and University of Alabama at Birmingham for the active or placebo arm.
- Secondary endpoints
  - CaCC and BK activity as measured by change in NPD upon ATP application (see above).
  - Change in sweat chloride concentration
  - FEV1 (absolute and relative changes)
  - Changes in serum inflammatory markers (hsCRP, WBC including absolute neutrophil count, % PMNs, SAA, calprotectin, GM-CSF, TGF- $\beta$  active and total)
  - Nasal cytokine changes (IL-1 $\beta$ , TGF- $\beta$  active and total, IL-6, IL-8 IL-13)
  - Quality of life questionnaire (CFQ-R)
  - Blood levels of losartan, EXP3179, and EXP3174 (17,18)
  - LRRC26 mRNA (correlates with BK activity *in vitro*) and TGF- $\beta$  mRNA expression in nasal cells by qPCR (while some contamination with other cells is possible, "purification" with for instance cell sorting

is not feasible given the small number of cells; we will assess purity after cytopsin with epithelial and other cell markers using immunofluorescence).

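### Secondary endpoints are compared by t-tests on changes with no baseline or site adjustment, and the plan leaves open whether log or square-root transforms apply to visit values or to changes

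*Combined protocol and SAP*

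**What the plan says.** In the statistics section, under the analysis of secondary endpoints, the distributions of the outcomes are to be examined first. The examples are "such as CaCC/BK activity, change in sweat chloride concentration, FEV1, changes in serum inflammatory markers, etc". The next sentence reads "Necessary transformations such as logarithmic or square root will be applied to satisfy normality assumptions if necessary". After a description of summary statistics at baseline, week 6 and weeks 13/14, the comparison is given: "t-tests for comparisons of the changes over the period between treatments will be conducted". Tests are two-sided at 0.05.

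The Endpoints section words several of these outcomes as changes: "Changes in serum inflammatory markers (hsCRP, WBC including absolute neutrophil count, % PMNs, SAA, calprotectin, GM-CSF" and, for the ATP response, "CaCC and BK activity as measured by change in NPD upon ATP application (see above". The sample size is given in Study Design and Methods: "This trial will be randomized 1:1 with placebo (n=18 for each group". Randomization is stratified by site, and the recruitment paragraph expects about 9 patients per site.

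The mixed model mentioned in the analysis paragraph is for the primary endpoint. For secondary endpoints no covariate is named. The same paragraph says that the main purpose is to estimate mean changes and their variability for a later trial. The section on expected results and limitations calls these endpoints exploratory.

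**The concern.** Three things are left loose in a short paragraph.

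- **Scale of the transform.** Two of the four examples are named as changes. A log or square root of a change does not exist when the change is negative, and the log fails at zero as well. If visit values are meant, the plan does not say so.
- **Timing of the choice.** The decision follows inspection of the trial's own data, endpoint by endpoint. The Study Drug section lists the biostatistics core among those who are unblinded, so nothing in the text separates this choice from knowledge of allocation.
- **No adjustment.** A change score subtracts the whole baseline instead of estimating how much of it carries over, and the stratification factor is ignored.

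At stake are the efficiency of the test of the secondary hypothesis on nasal cytokines and systemic markers and, more important for a pilot, the quality of the SDs handed to the next trial.

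**Working it through.** **Figures to reproduce.** None. The available text gives no SD, correlation, effect size or power for any secondary endpoint. All marker inputs below are assumptions. From the documents come n = 18 per arm and two-sided alpha 0.05.

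**Step 1: can the transforms be applied?** With no treatment effect and no drift, follow-up is as likely to lie below baseline as above it, so 50% of changes are negative: 0.5 × 36 = 18 patients per marker. For a log-normal marker with log-SD s at each visit and correlation ρ, the log change has SD s√(2(1−ρ)), which equals s at ρ = 0.5. If losartan halves the marker (ln 2 = 0.693), the share of negative changes in that arm is Φ(0.693/s):

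- s = 0.5: Φ(1.39) = 92%
- s = 0.7: Φ(0.99) = 84%
- s = 1.0: Φ(0.69) = 76%
- s = 1.3: Φ(0.53) = 70%

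Transforming changes is therefore not workable. Transforming visit values works for serum markers, nasal cytokines, sweat chloride and FEV1, which are positive.

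**Step 2: what does baseline adjustment buy?** With equal variance at both visits, the change has variance 2s²(1−ρ), and ANCOVA has residual variance s²(1−ρ²). Their ratio is (1+ρ)/2: 0.75 at ρ = 0.5 and 0.85 at ρ = 0.7. ANCOVA thus removes 25% or 15% of the variance. This holds on the original scale too, so it applies to the ATP response, sweat chloride, FEV1 and CFQ-R.

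**Step 3: power.** For the two log-scale methods the noncentrality is 0.693/(SD × √(2/18)). At s = 1.0 and ρ = 0.5:

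- Log change: 0.693/(1.000 × 0.333) = 2.08 on 34 df, power 52%.
- Log ANCOVA: SD = √0.75 = 0.866, so 0.693/(0.866 × 0.333) = 2.40 on 33 df, power about 64%.

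The raw-change t-test has no simple formula and was simulated (40,000 trials per row, no dropout, true halving, ρ = 0.5):

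| Log-SD | Raw-change t-test | Log-change t-test | Log ANCOVA |
|---|---|---|---|
| 0.5 | 84% | 98% | 99.6% |
| 0.7 | 51% | 82% | 91% |
| 1.0 | 24% | 52% | 63% |
| 1.3 | 12% | 34% | 43% |

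The formula and repeat simulations agree within about 2 points. With no effect, rejection rates are 3.3% to 4.6% for raw change and about 5% for both log-scale methods. ANCOVA here adjusts for baseline only. Adding four sites would leave 36 − 2 − 1 − 3 = 30 df instead of 33, a small cost.

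**Step 4: sensitivity.** At log-SD 1.0, ρ = 0.7 and a halving, the three figures are about 34, 74 and 80%. Smaller effects shrink the gap. At ρ = 0.5, going from raw change to log change gives:

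- ratio 0.7: 41 to 55% (log-SD 0.5) and 10 to 18% (log-SD 1.0)
- ratio 0.8: 50 to 58% (log-SD 0.3) and 7 to 10% (log-SD 1.0)

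**Step 5: the estimation aim.** The next trial's sample size is proportional to the variance estimated here. In the settings of the table, the ratio of the 90th to the 10th percentile of the pooled variance estimate is about 2.7, 3.7, 6.5 and 12.4 for raw change (log-SD 0.5, 0.7, 1.0, 1.3), against about 1.9 for log change throughout.

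**The case against.** The text is ambiguous rather than wrong. FEV1 is listed as a level, and the paragraph promises means at each visit as well as the change, so transforming visit values and then differencing fits the wording. On that reading the log change is a valid outcome. This stands.

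A reader might infer that skewed markers would end up in t-tests on raw changes. No sentence says so. The listed transforms are only examples, and the stated intent is to meet normality. The raw-change column above shows what is at risk if no workable transform is chosen, not what the plan commits to.

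A reader might also take the primary hypothesis, in which the response "will change by more than -4 mV using the most polarized nostril each time", as evidence that the ATP response is negative and cannot be logged. That figure is a between-arm effect on the primary endpoint. For ATP the documents give no sign convention. They describe the response as larger in CF and expected to fall. The handling of its sign is unspecified, and no more than that can be said.

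The size of the gain rests on assumed skew. WBC and % PMNs are also on the list, and strong skew is not shown for them. Part of the gap between the outer columns comes from baseline adjustment: 63 − 52 = 11 points at log-SD 1.0. Finally, the endpoints are exploratory and have no power target to miss. All of this limits the consequence. It does not supply the missing scale or covariates.

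**Conclusion.** The concern holds as a gap in specification together with an inefficient comparison. The plan commits secondary endpoints to t-tests on changes without baseline or site, and it permits transforms chosen after inspection without naming the scale. Applied to changes they would be undefined for about half the patients under no effect. Applied to visit values of positive markers they are sound.

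Under the assumptions stated (log-normal markers, true halving, correlation 0.5, no dropout), log-scale ANCOVA takes power from 84 to 99.6% at log-SD 0.5 and from 24 to 63% at log-SD 1.0 compared with raw change. Compared with a log change the gain is smaller: 98 to 99.6% and 52 to 63%. The gain is modest for mild skew and large for strong skew. The documents cannot settle which applies.

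They do not support the stronger conclusion that the trial will analyse raw changes. Since these endpoints are exploratory, the main benefit is more stable estimates for the later trial.

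**What to change.** Before unblinding, and before the biostatistics core (itself listed as unblinded) examines outcome data, replace the conditional transform and the t-tests by fixed rules:

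- **Positive, skewed markers** (such as hsCRP, SAA, calprotectin, GM-CSF, TGF-beta, nasal cytokines and mRNA): take logs of the value at each visit. Compare arms at the end-of-treatment assessment by ANCOVA with log baseline and site. Report geometric-mean ratios with 95% CIs, and the log-scale SD and correlation for planning.
- **ATP response, sweat chloride, FEV1 and CFQ-R**: keep the original scale, use ANCOVA with baseline and site, and state the sign convention for the ATP response.
- **WBC, neutrophil count and % PMNs**: assign each to one of the two groups now.
- **Values below the assay limit**: state one simple rule.

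The cost is wording in the statistics section, with no extra patients, visits or assays. Marker effects will be read as ratios rather than absolute changes, and the site terms use three degrees of freedom. Descriptive means and changes by visit can stay as planned.

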## **Data management**

Data collected will include demographics, clinical symptoms, CFQ-R, pulmonary function tests and NPD. Samples to be collected include nasal fluid (Leukosorb) and nasal cells at the beginning, during and at the end of the study. We will obtain blood for safety reasons (liver and renal function), for evaluation of an inflammatory marker (CBC w/ differential; CMP; CPK, CRP and other inflammatory markers). Blood for levels of losartan and metabolites (before next morning dose) will be also collected at the end of each treatment phase.

No personal identifiers will be collected and each patient's data will be coded. Data will be captured at secure password protected website (Red-Cap). Sites will be granted access to this database.

Monitoring will be provided by Clinical Research Operations & Regulatory Support (CRORS) monitoring group at the University of Miami.

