## List of assessments

VISIT	Visit 1	Visit 2	Visit 3 Phone call	Visit 3.a Phone call	Visit 4	Visit 5	Visit 6 Phone call	Visit 7	Visit 8
	-1 weeks	25 mg or 50 mg losartan/placebo	50 mg or 100 mg losartan/placebo	1 week ± 2 days	2 days ± 1 day from Visit 3	3 weeks ± 2 days	6 weeks ± 2 days	10 weeks ± 2 days	13 weeks ± 2 days
Informed consent	X								
Full medical history	X								
Intermittent history		X			X	X		X	X
Physical exam	X	X			X	X		X	X
Vitals	X	X			X	X		X	X
Pulse oximetry	X	X			X	X		X	X
Concomitant medications	X								
Changes in medications		X	X	X	X	X	X	X	X
CFQ-R	X					X		X	
Review adverse events, exacerbations		X	X	X	X	X	X	X	X
Spirometry	X					X		X	
CBC w/ differential; CMP; CPK, CRP and other inflammatory markers	X				X	X		X	
Blood for levels of losartan and metabolites (before next morning dose)						X		X	
NPD	X					X		X	
Leukosorb cytokine levels		X							X
Nasal cells		X							X
Sweat chloride		X							X
Serum or urine pregnancy test	X	X			X	X		X	X

IP dispensation: Visit 2 (3-week supply), visit 4 (3-week supply) and visit 5 (8-week supply)

## Appendix 2

CFQR Questionnaire:

More information:

<http://qol.thoracic.org/sections/instruments/ae/pages/cfq-cfq-r.html>

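### Between-arm tests of the secondary outcomes do not adjust for baseline as a covariate or for site, which is unbiased but can cost precision with at most 18 patients per arm

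*Combined protocol and SAP*

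**What the plan says.** The Analysis text under Statistics and Power Analysis treats primary and secondary endpoints separately. The mixed-effects model appears only in the primary-endpoint paragraph. For the secondary endpoints the plan gives descriptive summaries with 95% confidence intervals, and for the between-arm comparison it says that "t-tests for comparisons of the changes over the period between treatments will be conducted".

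Baseline has a descriptive role: "Baseline values of all variables will be examined, and estimates of baseline means and changes over time will be provided". No baseline covariate is named. The Randomization paragraph says "Participants will be stratified by site during randomization", but no site term appears in the secondary comparison.

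Appendix 1 (List of assessments) schedules a pre-treatment value for all but one group of the listed secondary outcomes:
- **Visit 1:** NPD (which includes the ATP response), spirometry, CFQ-R and blood markers.
- **Visit 2:** nasal cytokines, nasal cells and sweat chloride. The Intervention section starts drug only after baseline parameters are established.
- **No pre-treatment value:** losartan and metabolite levels, drawn at Visits 5 and 7 only.

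**The concern.** A t-test on change assumes that each unit of baseline carries over fully to follow-up. When the correlation between baseline and follow-up is low or moderate, subtracting the baseline adds its noise to the outcome. A model that estimates the slope removes that excess. Leaving site out puts any between-site variation in change into the error term, although the randomisation was balanced on site.

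The stake is the width of the intervals around the treatment differences. The plan says that the secondary results should give reliable estimates for designing later studies. The sample is at most 18 per arm, and the Removal of Subjects section does not replace withdrawals. The data needed for adjustment are already scheduled.

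**Working it through.** The plan states no SD, correlation or power for any secondary outcome, so there is no figure of its own to reproduce. Results are relative to the planned t-test on change.

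**Inputs from the documents.** 36 patients, 18 per arm (Study plan); about 9 per site (Recruitment and Informed Consent), hence 36/9 = 4 sites; two-sided 5% level (Analysis).

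**Assumptions.** Correlation rho between baseline and follow-up; ratio k of follow-up SD to baseline SD; normal baseline with a common slope; each site split 5/4 between arms; no true site effect unless stated.

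**Step 1: planned test.** 95% half-width = t(34) × sqrt(2/18) = 2.032 × 0.333 = 0.677 change SDs.

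**Step 2: effect of estimating the slope.** With baseline variance 1, the change variance is 1 + k² − 2·rho·k and the ANCOVA residual variance is k²(1 − rho²). The difference is (1 − rho·k)², which is never negative. With k = 1 the ratio of ANCOVA to change variance is (1 + rho)/2.

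**Step 3: cost of estimating the terms at N = 36.**
- Baseline slope, with three site terms also in the model: variance × (1 + 1/(36 − 7)) = 30/29 = 1.0345.
- Site terms: a 5/4 split gives information 4 × (5×4/9) = 8.889, against 18×18/36 = 9 without site, so variance × 9/8.889 = 1.0125.
- Degrees of freedom fall from 34 to 30: t(30)/t(34) = 2.042/2.032 = 1.005.

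**Step 4: interval width of ANCOVA with baseline and site, relative to the t-test (k = 1).** Ratio = sqrt[(1 + rho)/2 × 1.0345 × 1.0125] × 1.005.

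| rho | (1 + rho)/2 | width ratio | half-width (change SDs) |
|---|---|---|---|
| 0.3 | 0.65 | 0.83 | 0.56 |
| 0.5 | 0.75 | 0.89 | 0.60 |
| 0.7 | 0.85 | 0.95 | 0.64 |
| 0.9 | 0.95 | 1.00 | 0.68 |

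Simulation (4 sites of 9, no site effect) gave mean width ratios of 0.83, 0.89, 0.95 and 1.00. Type I error for the adjusted analysis was 4.3 to 5.4%.

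**Step 5: unequal SDs.** Variance ratios with baseline alone, which include the slope factor 33/32:

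| k | rho 0.3 | 0.5 | 0.7 | 0.8 | 0.9 |
|---|---|---|---|---|---|
| 1.25 | 0.81 | 0.92 | 1.01 | 1.03 | 0.98 |
| 0.8 | 0.52 | 0.59 | 0.65 | 0.66 | 0.63 |

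**Step 6: worst average case.** Adjustment gains nothing when rho·k = 1 (for example k = 1.25, rho = 0.8) and sites do not differ. The width ratio is then sqrt(1.0345 × 1.0125) × 1.005 = 1.028, and simulation gave 1.027. With 30 completers (an assumption) the figure is somewhat over 3%.

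**Step 7: site alone.** Adding site to the change analysis widens the interval by about 1.0% if change does not differ by site. It breaks even when about 2% of the change variance lies between sites. The documents do not show which case applies. When site was assumed to explain 20% of residual variance, the t-test without site was conservative (type I error 3.5 to 4.1%).

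**The case against.** The strongest reply is that this affects only exploratory comparisons. The Expected Results section calls the secondary endpoints exploratory, and the Analysis text puts estimation of mean changes and variability ahead of the tests. The planned means, SDs and intervals already serve that aim, and several endpoints are themselves defined as changes. This stands as a limit on priority. It does not remove the point, because the plan still promises these between-arm tests and their estimates are meant to inform later trials.

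The second reply is that the gain is unknown. This is right: at a correlation near 0.9 there is none. The 3% cost is also an average and does not bound what happens in one trial. In simulation with equal SDs and no site effect, the adjusted interval was the wider one in about 40% of trials at a correlation of 0.8 and about 10% at 0.5. The site term rests on less than the baseline term.

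A reader might infer more than the documents support:
- **That baseline is ignored.** A change score already subtracts it; what is missing is the covariate.
- **That the tests are biased or too liberal.** In simulation under no effect, the change t-test centred on zero, and omitting site made it conservative.
- **That the timing of samples undermines the point.** The Analysis text promises "Means at baseline, 6 and 13/14 weeks, for each outcome, as well as the change over time will be provided", while Appendix 1 has sweat chloride and nasal samples at Visits 2 and 8 only. That mismatch is a separate matter, since a pre-treatment value exists under every reading.
- **That the primary endpoint is affected in the same way.** Its formal analysis is a mixed model, and no loss is claimed there.

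**Conclusion.** The point holds as a question of efficiency. The planned secondary comparisons are unbiased under randomisation with complete data, but they can give up precision that data already scheduled would recover. Under the equal-SD assumption the saving ranges from about 17% of interval width to nothing over correlations of 0.3 to 0.9. It is larger if follow-up varies less than baseline. The price is about 2.7% of width in the worst average case with 36 patients, and somewhat over 3% with 30 completers. All of this rests on assumed correlations, SD ratios and site effects, because the documents supply none. The figures are for a single-follow-up ANCOVA and say nothing about repeated-measures models. The priority is minor.

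**What to change.** For each secondary outcome with a pre-treatment value, state that the between-arm comparison is an ANCOVA of the final scheduled value on treatment, baseline and site, with baseline on the same scale as the outcome if it is transformed. State in advance how a site with very few patients will be pooled. Keep the planned unadjusted mean changes, SDs and 95% confidence intervals, which later trial planning needs. Leave losartan and metabolite levels descriptive.

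This is a change of SAP wording, with no new visits or data. It uses 4 further degrees of freedom (34 to 30).
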